## TERMS, DEFINITIONS, AND ABBREVIATIONS

Terms/Abbreviations	Definition
AE	Adverse Event
CI	Cochlear Implant
Charge	Unit of electrical stimulation
Custom Sound™	Clinical programming software for Nucleus cochlear implant systems
Facilitated MAP	A MAP programmed remotely with the assistance of a facilitator
Facilitator	A trained staff member at the programming site
IDE	Investigational Device Exemption
Live Programming	Traditional face to face programming interaction between a recipient and an audiologist at the same physical location
MAP	A program that defines the individualized parameters of recipients for a specific speech coding strategy
Nucleus® 5 Sound Processor	BTE sound processor to be used in the evaluation
Nucleus® 6 Sound Processor (CP910 or CP920)	BTE sound processor to be used in the evaluation
Primary Audiologist	The audiologist who regularly provides programming services to the subject
Remote Programming	A programming interaction between a recipient and an audiologist that occurs via telecommunication technology when the two parties are at different physical locations
Self MAP	A MAP programmed remotely without the assistance of a facilitator

## STUDY SUMMARY

Title	Investigation of consistencies and performance of cochlear implant MAPs programmed via telecommunication
Study Sites	Up to 5 North American centers
Study Duration	Up to 12 months
Study Time	3-4 months for each subject
Study Population	Up to 40 subjects aged 12 years or greater
Design Overview	The study will be conducted in a repeated measures design
Primary Objective	To demonstrate the safety and efficacy of CI programming via telecommunication.
Study Intervals	
Visit 1 (at least 1 month but no more than 12 months after a regular programming session)
 
Visit 2 (within one month after Visit 1)
 
Visit 3 (2-4 weeks after Visit 2)
 
Visit 4 (2-4 weeks after Visit 3)
 
Visit 5 (2-4 weeks after Visit 4)

Primary Safety Endpoint	Characterize the safety profile of device and/or procedure related adverse events associated with facilitated remote MAP programming, unassisted MAP programming and audiologist live MAP programming
Co-Primary Efficacy Endpoints	
 
1. Demonstrate that performance on CNC words using a remotely programmed facilitated MAP is no worse than when using a live programmed MAP
 
2. Demonstrate that performance on CNC words using an unassisted remotely programmed MAP is no worse than when using a live programmed MAP
 

Secondary Efficacy Endpoint	Demonstrate non-inferiority of unassisted remote MAP programming compared to facilitated MAP programming via performance on CNC words.

## INTRODUCTION

Telemedicine is the practice of using technology to provide remote clinical services over the internet. In that cochlear implantation requires regular programming visits with an audiologist, the use of telemedicine can prove valuable and efficacious for recipients, particularly those who live far from clinics, have limited transportation options, or are medically fragile. Telemedicine can also be utilized for direct high level trouble shooting between recipients, clinicians, specialists, and manufacturers.

Primary medicine and some of its auxiliary services have already entered into the arena of telepractice with successful outcomes (Uscher-Pines, et al., 2014; Darkins, et al., 2013; Mashima & Doarn, 2008). Staying on track with this technological advent, resourceful clinicians and researchers have begun exploring the validity of remote audiological intervention. Documented outcomes suggest comparable results between traditional live programming and remote programming measures (Eikelboom, 2014; McElveen, 2010; Ramos, 2009; Rodriguez, 2014; Samuel, 2014; Wesarg, 2010). Performance validation of remotely programmed maps as examined by Hughes (2012) and Goehring (2012) denotes that any changes in speech perception scores may be a result of sub-optimal testing environments as opposed to programming delivery method. Furthermore, when probed, most study participants reported satisfaction with the remote programming sessions, and indicated they would be interested in utilizing the technology for future appointments.

Some points of interest that have arisen include the capacity to assess physical integrity of devices, detection of adverse events over a telecommunication medium, remote programming in the pediatric population, duration of CI use prior to remote sessions, professional state licensure requirements, and reimbursement. These topics should be considered for future investigation.

Given that telemedicine is being widely utilized, and studies show minimal to no change in aided thresholds and MAP Threshold (T) and Comfort (C) levels, this investigation aims to validate the safety and efficacy of remote cochlear implant programming in an effort to establish clinical support for this practice and subsequently increase access to recipients. Specifically, this study will show that speech recognition scores obtained using remotely programmed MAPs are no worse than those obtained using live programmed MAPs. Additionally, it will demonstrate that live MAPping adverse events are consistent with and not inferior to remote MAPping adverse events. Finally, this study will capture overall electrical charge of remotely programmed MAPs, and explore any inconsistencies between the audiologist-to-facilitator model and the audiologist-to-recipient model of remote service delivery.

## **STUDY OBJECTIVES**

### **Primary Objectives**

The primary objective of this multi-site study is to investigate the safety and efficacy of programming cochlear implants through telecommunication.

Safety will be determined by characterizing the safety profile of device and/or procedure related adverse events associated with facilitated remote MAP programming, unassisted MAP programming and audiologist live MAP programming. An adverse event (AE) is the development of an untoward medical occurrence or the deterioration of a pre-existing medical condition following or during exposure to an investigational product, whether or not considered causally related to the product.

Efficacy will be determined by showing that performance on the CNC word recognition test using a remotely programmed MAP is no worse than when using a live programmed MAP.

## **INVESTIGATIONAL PROTOCOL**

### **Subject Selection**

The proposed investigation will take place in the United States. Up to 5 clinical sites and up to 40 subjects will be enrolled. Due to time needed for site training and subject recruitment, the total duration of this multi-site study will be 12 months.

### **Inclusion Criteria**

- Individuals aged greater than 12 years that are native English speakers and are capable of completing the study evaluation as deemed by their primary audiologist
- Unilateral or bilateral cochlear implant recipients of a CI24RE, CI422 or CI500 series implant who are in possession of a backup sound processor
- A minimum of 12 months' experience with a CP800 or CP900 series sound processor, and current MAP programmed within 12 months prior to Visit 1
- Willingness to participate in and to comply with all requirements of the protocol
- Able to demonstrate protocol competence as confirmed by primary audiologist

### **Criteria for Exclusion**

- Unrealistic expectations on the part of the subject, regarding the possible benefits, risks, and limitations of remote service delivery
- Unwillingness or inability of the candidate to comply with all investigational requirements
- Additional handicaps that would prevent or restrict participation in the audiological evaluations

- Inability to demonstrate basic technological skills for simple computer-based tasks and device connecting after training by primary audiologist

## Investigational Procedures

### Design Overview

Cochlear implant recipients aged greater than 12 years of age will be asked to participate in this clinical study. A single-subject research design (in which each subject serves as his or her own control) is appropriate since it accommodates the heterogeneity that characterizes hearing-impaired populations. Subjects will be tested at three intervals: the first, third, and last of five total visits.

At **Visit One**, the subjects will be screened and consented by their primary audiologist. They will complete speech testing in the unilateral condition, using their current MAP which they must have been using for no more than 12 months. Subjects will schedule Visit 2 to fall within one month after Visit 1.

**Visit Two** will take place at a pre-determined site, different than the subject's primary programming center. The subjects will participate in a remote location programming session conducted by their primary audiologist via telecommunication, with on-site assistance provided by a trained facilitator. This MAP will be referred to as the Facilitated MAP.

Subjects will return home and use this new program for 2-4 weeks, after which time they will return to their primary programming center for Visit 3.

For **Visit Three** (2-4 weeks after Visit 2), subjects will return to their primary programming center for speech testing using their remotely programmed MAP (Facilitated MAP), and to complete a comparative survey.

**Visit Four** will occur 2-4 weeks after Visit 3 at the same pre-determined site as Visit 2. The subjects will participate in a second remote programming session conducted by their primary audiologist via telecommunication, but the subject will serve as his or her own facilitator. This MAP will be referred to as the Self MAP.

Subjects will return home and use this new program for 2-4 weeks, after which time they will return to their primary programming center for Visit 5.

At **Visit Five**, subjects will complete speech testing using their second remotely programmed MAP (Self MAP). Subjects will also complete a comparative survey and a questionnaire regarding their experience with remote programming.

The following study procedures will be completed:

## **MAP Programming Methods**

Subjects will be programmed at a remote clinic location by their primary audiologist programming via telecommunication. The subjects' existing "familiar" MAP will remain in slot #1. Audiologists will save each remotely programmed MAP into slot #2, overwriting any previous program in that slot (subjects will be able to have their choice of program re-entered into slot #2 after they have completed participation in this study). Audiologists will anonymize and export the MAP to the sponsor after each programming session.

## **System Requirements**

Each remote site will require a programming computer, a programming pod, and a programming cable. Computers will be outfitted with a password locked Custom Sound application to allow software access to the remote audiologist meanwhile preventing any accidental programming by the recipient. Each site will also need microphone/speaker/camera capabilities on the computer for communication between the audiologist and the subject during the remote sessions. A wired or wireless internet broadcasting system is acceptable with a minimum connection speed of 1 megabit/sec in both directions.

The programmer site will require the same computer, software, and connection specifications as outlined above.

## **Speech Perception Testing**

Speech perception testing will be completed at Visit One, Visit Three, and Visit Five.

Speech perception testing to evaluate the program settings will be assessed in the unilateral condition (cochlear implant ear only) and the contralateral ear will be plugged (or the contralateral CI will be removed if applicable).

Speech perception testing will be completed at the subject's primary clinic site, and evaluation lists will be randomized.

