## **Evaluation Materials and Test Conditions**

- At Visit One, Visit Three, and Visit Five, participants will have their speech perception tested using CNC words (Peterson & Lehiste, 1962) in quiet presented at 60 dBA as indicated in Figure 1.
- Each participant will complete 2 full lists (50 words per list) per test condition

For the purpose of evaluating the remotely programmed MAPs, test condition refers to a program slot number:

1. Test condition: Familiar program – Program 1: Participant's current program that he/she was utilizing prior to the remote MAPping (Tested at Visit 1)

2. Test condition: Remote program – Program 2: the Facilitated MAP programmed remotely at Visit 2 (tested at Visit 3) and the Self MAP programmed remotely at Visit 4 (tested at Visit 5).

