### Test Materials:

- CNC word list presented at 60 dBA (subject facing speaker) with contralateral ear plugged. Two lists (of 50 words each) will be completed for each condition. Score each test condition for % of words correct.

**Note:** The test material lists will be randomized.

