7 STUDY POPULATION

The study population will include up to 40 subjects (12 years of age or older) who have unilateral or bilateral cochlear implants and are capable of completing the study evaluation.

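### For unilateral recipients, the implant-ear CNC score is isolated by an earplug alone, so any words recognised through the plug dilute a remote-MAP loss and favour non-inferiority

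*Protocol*

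**What the plan says.** **Test condition.** Protocol, Speech Perception Testing: the programs "will be assessed in the unilateral condition (cochlear implant ear only) and the contralateral ear will be plugged". The same sentence provides for removing a contralateral implant where there is one. Under Endpoint Testing, the Test Materials text repeats the plug: "CNC word list presented at 60 dBA (subject facing speaker) with contralateral ear plugged". Evaluation Materials and Test Conditions has the words presented "in quiet presented at 60 dBA as indicated in Figure 1". That figure is missing from this copy.

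**Who is tested.** The Inclusion Criteria admit "Unilateral or bilateral cochlear implant recipients of a CI24RE, CI422 or CI500 series implant who are in possession of a backup sound processor". SAP section 7 describes subjects "who have unilateral or bilateral cochlear implants and are capable of completing the study evaluation". The closest exclusion is "Additional handicaps that would prevent or restrict participation in the audiological evaluations", which does not concern hearing in the other ear. No criterion in either document limits contralateral hearing.

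**What is not in the visible text.** There is no muff, masking, contralateral audiogram or implant-off check, and the SAP has no analysis by contralateral hearing.

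**How the score is used.** SAP sections 10.2 and 10.3 test within-subject differences in CNC score. Success requires the upper limit of the two-sided 95% confidence interval to lie below 10 points.

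**The concern.** A plug attenuates sound but does not exclude it. A unilateral recipient with useful acoustic hearing in the other ear may still recognise some words at 60 dBA. Such a word is scored correct whichever MAP is in use, so a loss caused by the remote MAP on that word is never counted.

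The within-subject design does not remove this. A constant added to both scores would cancel in the difference. Here the other ear rescues some of the words that the implanted ear misses, so it rescues more when the implanted ear does worse. The difference is compressed rather than shifted.

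In a superiority trial, compression toward 0 would be conservative. In a non-inferiority trial it works in favour of success. It acts on Live minus Facilitated, Live minus Unassisted and Facilitated minus Unassisted alike. The randomised lists and the multiple imputation in SAP section 14 neither detect nor correct it.

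**Working it through.** **Inputs from the documents** (Protocol, Sample Size; SAP sections 8 and 10.2): one-sided alpha 0.025, SD of differences 15 points, margin 10 points, planned n = 40, one-sample t-test on the differences.

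**Assumed inputs** (in neither document): f, the share of all subjects who recognise words through the plug; and c, the CNC score those subjects would obtain through the plugged ear alone.

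**Step 1: reproduce the plan's figure.** The probability of passing with true mean difference d is

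P(T > t(0.975, n-1)), where T is non-central t with n-1 degrees of freedom and non-centrality (10 - d)·√n / 15.

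With d = 0, n = 25 gives 89.2% and n = 26 gives 90.4%. The stated minimum of 26 is reproduced. n = 40 gives 98.4%. The sample size is not in dispute.

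**Step 2: dilution.** Treat the two ears as independent (an assumption). If the implanted ear scores p, the mixed score is 1 - (1-p)(1-c). An implant-ear loss L is then observed as L(1-c) in an affected subject. Averaged over all subjects, the observed loss is L(1 - f·c).

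**Step 3: chance of passing when the true implant-ear loss equals the margin.** Set L = 10, so d = 10(1 - f·c), and hold the SD at 15 with n = 40. For f = 10% and c = 50%, d = 10(1 - 0.05) = 9.5. The non-centrality is 0.5·√40/15 = 0.211, and the chance of passing is 4.0%. With no leakage it is 2.5%.

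| f (of 40) | c = 20%: d, chance | c = 50%: d, chance | c = 100%: d, chance |
|---|---|---|---|
| 5% (2) | 9.9, 2.7% | 9.75, 3.2% | 9.5, 4.0% |
| 10% (4) | 9.8, 3.0% | 9.5, 4.0% | 9.0, 6.1% |
| 20% (8) | 9.6, 3.6% | 9.0, 6.1% | 8.0, 12.8% |

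The last column is an upper bound: an affected subject shows no loss at all.

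**Step 4: sensitivity to the assumptions.** Larger shares give larger effects: 7.4% at f = 25%, c = 50%, and 17.6% at f = 50%, c = 50%. A smaller SD also matters. With SD 10, f = 25% gives 4.9% at c = 20% and 11.7% at c = 50%.

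**The case against.** **The size is assumed.** Neither document gives the attenuation of the plug, the contralateral hearing of the subjects or the share affected. Nothing shows that even one subject would be affected. Bilateral recipients fall outside the problem, which lowers f. This stands, and it limits the claim about size. It does not remove the gap, because the plan collects nothing that would reveal f or c afterwards.

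**A reader might infer that a remote-MAP loss is concealed outright.** The documents do not support that. Complete concealment needs a plugged-ear score of 100% in every affected subject. Partial recognition only dilutes the loss, and for c of 20-50% at shares of 5-10% the chance of passing stays within about 1.5 points of 2.5%.

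**A reader might also infer that a bilateral recipient's second implant stays on,** because the Test Materials text mentions only the plug. The section that governs testing says the condition "will be assessed in the unilateral condition (cochlear implant ear only) and the contralateral ear will be plugged (or the contralateral CI will be removed" where applicable. Test Materials is a shorter restatement and does not contradict it.

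**Figure 1 may show more.** It is titled as the test setup and cannot be seen here, so the statement that nothing beyond a plug is specified applies to the visible text only.

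**The plan does prescribe a method,** with no visit-specific variation. That is true, but using the same plug each time does not cancel the compression.

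**Conclusion.** The point holds for unilateral recipients who can recognise words through the plug. For them, the recorded score is not the implant-ear score the protocol defines, and the error favours non-inferiority in both co-primary tests and in the secondary test.

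Over shares of 5-20% and plugged-ear scores of 20-50%, the chance of passing one co-primary at a true loss of exactly 10 points lies between 2.7% and 6.1%, against 2.5% with full isolation. The bound under complete concealment is 4.0-12.8% over the same shares. These figures rest on assumed f and c, independent ears, and the plan's SD of 15 held fixed.

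This is an inexpensive improvement in measurement. It is not an error in the sample size or the test, and it does not show that the trial's conclusion would be wrong.

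**What to change.** 1. In Speech Perception Testing and in Test Materials, state one identical rule: a non-implanted contralateral ear is occluded with a plug plus circumaural muff, or masked, in the same way at Visits 1, 3 and 5. Keep the existing removal of a contralateral implant, and repeat it in Test Materials so that the two texts match. If Figure 1 already shows more than a plug, carry that into the text.
2. At Visit 1, with the implant off and the other ear occluded, record whether words at 60 dBA are recognised. A few words are enough. This has to be collected prospectively.
3. Add to the SAP a sensitivity analysis of both co-primary endpoints that omits subjects who recognise words in that check, reporting the mean difference and its 95% confidence interval against the same margin.

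Cost: a muff or masking noise, about two minutes at Visit 1, and one extra table. The sensitivity analysis has slightly fewer subjects. If 8 of 40 were omitted, 32 would remain before attrition, still above the stated minimum of 26. The planned sample size and primary tests do not change.

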## **Evaluation Materials and Test Conditions**

- At Visit One, Visit Three, and Visit Five, participants will have their speech perception tested using CNC words (Peterson & Lehiste, 1962) in quiet presented at 60 dBA as indicated in Figure 1.
- Each participant will complete 2 full lists (50 words per list) per test condition

For the purpose of evaluating the remotely programmed MAPs, test condition refers to a program slot number:

1. Test condition: Familiar program – Program 1: Participant's current program that he/she was utilizing prior to the remote MAPping (Tested at Visit 1)

2. Test condition: Remote program – Program 2: the Facilitated MAP programmed remotely at Visit 2 (tested at Visit 3) and the Self MAP programmed remotely at Visit 4 (tested at Visit 5).

**Figure 1: Test Setup for Speech Recognition Testing**

### **Self-Assessment/Subjective Questionnaires**

The following subjective questionnaire will be completed at Visit 2 and Visit 4 after the remote programming session.

#### ***Remote Programming Satisfaction Survey***

This in-house survey uses a satisfaction rating scale to gather subjects' opinions regarding the ease, quality, and comfort of the remote programming sessions.

The following self-assessment/subjective questionnaires will be completed at Visit 3 and Visit 5, following home use of the remotely programmed MAPs.

#### ***The Speech, Spatial and Qualities of Hearing Questionnaire – C (SSQ – C)***

The SSQ-C (Gatehouse & Noble, 2004) will be used as a subject self-assessment in three categories (speech hearing rating scale, spatial hearing rating scale, and sound qualities rating scale). The SSQ-C is the "comparative" version of the SSQ. It can be used for comparing two different hearing technologies. In this study, the SSQ-C will compare the subject's familiar map (Program #1) and a remote MAP located in Program slot #2.

The following subjective questionnaire will be completed at the final visit (Visit 5).

#### ***Telemedicine Experience Questionnaire***

This in-house survey was specifically designed to examine subjects' evaluations of the telemedicine experience. It includes a response rating scale, as well as the opportunity for open ended feedback.

## **Methods**

### **VISIT 1**

Step 1: Subject will arrive at his/her primary programming center. No programming will be completed at this visit.

Step 2: The subject will read and sign the informed consent form.

Step 3: The subject's primary audiologist will orient him/her to the programming equipment, detailing how to hook up the speech processor to the computer, how to launch the necessary applications, and how to utilize the chat function. The subject will demonstrate competency in these steps as deemed appropriate by the audiologist.

Step 4: Speech perception testing will be completed using Program 1 (subject's familiar program).

Step 5: The cdx file for the subject's current MAP will be anonymized and exported to the sponsor.

